4.1.4 Secondary care assessment

All participants will be seen in specialist rheumatology research clinics. If the participant does not attend their scheduled appointment they will be contacted by email, text and/or telephone to reschedule. If the participant is still unresponsive after up to 3 attempts to contact then the GP will be informed of their withdrawal from the study.

Page 28 of 53 IDEAL BACKPACS Protocol Final Version 1.1 date 09-Oct-2024

The secondary care assessment will consist of:

- Clinical assessment
- Blood sample collection
- X-ray
- Research MRI scan (likely to be a separate appointment)

On arrival at the local secondary care research clinic, if participants have not completed the study questionnaire electronically, they will be asked to do so as part of their consultation. There may be an option to complete a paper version of the questionnaire.

At the clinic appointment, an appropriately trained member of the clinical team will perform the semi-structured clinical research assessment (30 minutes for clinical assessment and 30-60 minutes for bloods and x-ray), evaluating axSpA features, using a standardised proforma listed in Table 6.

Participants will be asked if they have had a spinal/SIJ MRI scan in the last 12 months, if this is the case then the participant's previous MRI result will be assessed alongside the results of the research MRI scan.

Table 6: axSpA features evaluated in secondary care clinical assessment

axSpA feature	Method of assessment	Definition
Clinical assessmen	nt	
Peripheral arthritis	66/68 peripheral joint assessment	66/68-Swollen and Tender Joint Counts (SJC66/TJC68) Joints assessed include temporomandibular joint, (0-2) Sternoclavicular joint (0-2), Acromioclavicular joints (0-2), Glenohumeral(s) (0-2), Elbow(s) (0-2), Wrist(s) (0-2), Metacarpal phalangeal joints (0-10), Finger Proximal interphalangeal joint (0-10), hip(s) (tender score only 0-2), knee(s) (0-2), ankle(s) (0-2), metatarsal phalangeal joints (0-10), toe PIP(s) (0-10) The joint count is scored as a sum of the swollen joints (0-66) and the sum of the tender joints (0-68)
	Dactylitis count	Past or present dactylitis diagnosed by a physician (categorised as present/absent) with current dactylitis count 0-20 ref
	Heel enthesitis	Presence of Achilles Tendonitis and/or Plantar Fasciitis
	Enthesitis	Spondyloarthritis Research Consortium of Canada (SPARCC) Enthesitis Index

Page 29 of 53

IDEAL BACKPACS Protocol Final Version 1.1 date 09-Oct-2024

		and Leeds Enthesitis Index (LEI)
		16 sites assessed in total: the greater trochanter, quadriceps tendon insertion into the patella, patellar ligament insertion into the patella and tibial tuberosity, Achilles tendon insertion, plantar fascia insertion, medial and lateral epicondyles, and the supraspinatus insertion. Presence or absence of tenderness; max
		score = 16
Mobility	Bath Ankylosing Spondylitis Metrology Index (BASMI)	Index comprising 5 measures of spinal and hip mobility
Personal history	 a. Onset of chronic back pain symptoms b. Dactylitis c. Enthesitis d. Skin/nail psoriasis, e. Colitis f. Uveitis g. Anterior chest pain 	Self-reported, current and previous
Family history	Presence in first degree or second- degree relatives* of any of the following: a. Skin/nail psoriasis b. Colitis c. Uveitis, d. axSpA, e. Reactive arthritis, f. PsA	Self-reported (yes/no) and number of relatives affected
Response to NSAIDs	Only if NSAID response is not completely clear. At least one week at max tolerated dose. (If NSAID response if not completely clear) for individuals with no contraindications, min 7-day course of full dose NSAIDs (with telephone evaluation of NSAID response from research team at 1 week)	Self-reported (yes/no)

Page 30 of 53 IDEAL BACKPACS Protocol Final Version 1.1 date 09-Oct-2024

Blood tests	Blood tests			
Diagnostic laboratory tests	HLA-B27	Positive testing according to standard laboratory techniques.		
	CRP	C-reactive protein above upper normal limit in the presence of back pain, after exclusion of other causes for elevated CRP concentration.		
Imaging				
x-ray	Conventional SIJ plain x-rays	Modified New York criteria for each SIJ		
MRI	SIJ and whole spine (30 min scan) arranged within 4 weeks** of clinical assessment.	 (i) Description of oedema and structural features (fat metaplasia, erosions, ankylosis) in SIJs – yes/no for each. Interpretation according to ASAS specifications (bone marrow oedema in typical location 'highly suggestive' of axSpA) - yes/no for MRI positivity (ii) Are there unequivocal features of spinal inflammation? (yes/no) (iii) Overall impression across x-ray and MRI – (a) normal (b) equivocal (c) axSpA (d) other 		

^{*}First degree relative includes an individual's parents, siblings and children. Second degree relative includes grandparent, grandchild, half siblings, aunt/uncle and niece/nephew. **where possible, waiting times may vary between sites.

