3.1.3 Index tests

Index tests are the BACKPACS model (to be developed within this study) in addition to existing referral strategies described in Table 3.

Page 17 of 53 IDEAL BACKPACS Protocol Final Version 1.1 date 09-Oct-l2024

Table 3: Index tests

Index tests	Assessment
The Baraliakos strategy [9]	Assesses 3 clinical variables. If 2 or 3 of these variables are present (or a 'second step' HLA-B27 test is positive) then secondary care referral is suggested:
	 improvement in pain with NSAIDs after 48 hours raised CRP (blood test)
	• early morning stiffness (≥ 30minutes)
	This strategy requires follow up after the initial primary care clinic appointment.
The Modified Braun strategy [45]	Assesses 10 clinical variables and if at least 4 of these 10 variables are present then secondary care referral is suggested:
	 low back pain that started before the age of 35 years waking during the second half of the night because of symptoms buttock pain
	 improvement with movement improvement with non-steroidal anti-inflammatory drugs (NSAIDs)
	 a first-degree relative with spondyloarthritis, current/past arthritis,
	• current/past enthesitis
	current/past psoriasisHLA-B27 genetic test
The 'Assessment of SpondyloArthritis international Society (ASAS) strategy [44]	Patients with chronic backpain (≥ 3 months) with onset before 45 years, should be referred if at least one clinical variable is present:
1	Inflammatory backpain HLA-B27 positive
	 Sacroiliitis on imaging, if available (x-ray or MRI) Peripheral manifestations (arthritis, enthesitis and/or dactylitis)
	 Extra-articular manifestations (psoriasis, inflammatory bowel disease and/or uveitis) Family history for spondyloarthritis
	Good response to NSAIDS Acute elevated phase reactants (c-reactive protein or erythrocyte sedimentation rate)
The CaFaSpA referral strategy[15]	Easy to use and was developed in a primary care setting but was not adopted by NICE spondyloarthritis clinical guideline[3], as the study cohort reported a much lower than expected prevalence of HLA-B27 positive individuals. The explanation for this may be related to the study having a lengthy retrospective recruitment time

Page 18 of 53 IDEAL BACKPACS Protocol Final Version 1.1 date 09-Oct-l2024

for individuals with CBP (median 10 years), whilst
excluding patients diagnosed with axSpA during this
period; many of the excluded individuals with axSpA
would have been HLA-B27 positive. This approach

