86. Braun V, Clarke V: Using thematic analysis in psychology. Qualitative Research in Psychology

2006, 3(2):77-101.

- 87. Braun VC, V.: Thematic analysis. Research methods in social sciences: An A-Z of key concepts: Open University Press.; 2021.
- 88. Creswell JW, Miller DL: Determining Validity in Qualitative Inquiry. Theory Into Practice 2000, 39(3):124-130.

Appendices

Appendix 1: Specification of the variables used for the ASAS-Criteria for classification of Axial Spondylarthritis

Clinical Feature of axSpA	Definition
Inflammatory back pain (IBP)	IBP according to experts: 4 out of 5 of the
, , , , , , , , , , , , , , , , , , ,	following parameters present:
	1. Age at onset < 40 years
	2. Insidious onset
	3. Improvement with exercise
	4. No improvement with rest
	5. Pain at night (with improvement upon getting up)
Good response to NSAIDs	24-48 hours after a full dose of a non-steroidal
	anti-inflammatory drug (NSAID) the back pain is
	not present any more or much better.
	(the clinical co-applicants on the PGfAR IDEAL
	grant have concluded that response after one
	week would be more appropriate)
Arthritis	Past or present active synovitis diagnosed by a physician.
Dactylitis	Past or present dactylitis diagnosed by a
	physician.
Enthesitis	Heel enthesitis: past or present spontaneous
	pain or tenderness at examination of the site of
	the insertion of the Achilles tendon or plantar
	fascia at the calcaneus.
	(a broader evaluation of enthesitis is also being
	evaluated for the IDEAL study cohort)
Psoriasis	Past or present psoriasis diagnosed by a
	clinician.
Inflammatory bowel disease (IBD)	Past or present Crohn's disease or ulcerative
	colitis diagnosed by a physician.
Uveitis anterior	Past or present uveitis anterior, confirmed by an
	ophthalmologist.
Family history	Presence in first-degree or second-degree
	relatives of any of the following:
	a. Ankylosing spondylitis
	b. Psoriasis
	c. Uveitis
	d. Reactive arthritis
	e. IBD
HLA-B27	Positive testing according to standard laboratory
	techniques.
Elevated CRP	C-reactive protein above upper normal limit in
	the presence of back pain, after exclusion of
	other causes for elevated CRP concentration.

Page 53 of 53 IDEAL BACKPACS Protocol Final Version 1.1 date 09-Oct-2024

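### Table 6 does not list the past-arthritis and degree-of-relative fields that modified Braun needs; the first gap also reaches the secondary reference standard

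*Protocol*

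**What the plan says.** Section 4.1.4 of the protocol says that the clinical assessment follows a standardised proforma, which it gives as Table 6. Three rows of that table matter here.

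- **Peripheral arthritis.** The method is a 66/68 joint examination, labelled SJC66/TJC68. After a list of joints with a range for each, the cell states: "The joint count is scored as a sum of the swollen joints (0-66) and the sum of the tender joints (0-68".
- **Personal history.** This is self-reported and covers both current and previous episodes. The items are: "a. Onset of chronic back pain symptoms b. Dactylitis c. Enthesitis d. Skin/nail psoriasis, e. Colitis f. Uveitis g. Anterior chest pain".
- **Family history.** The row covers first- and second-degree relatives together, and the response is: "Self-reported (yes/no) and number of relatives affected". A footnote defines the two degrees.

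Two other places say how these features are to be used. Among the ten modified Braun items, Table 3 (Section 3.1.3) lists: "a first-degree relative with spondyloarthritis, current/past arthritis". Appendix 1, which specifies the variables of the ASAS classification, defines arthritis as: "Past or present active synovitis diagnosed by a physician". Its family-history item accepts relatives of either degree. Section 3.1.2 makes the ASAS classification the secondary reference standard.

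**The concern.** A rule can be scored only from what the form records. If Table 6 is used as written, a participant whose arthritis has resolved has no place on the form to report it. A participant with one affected relative is recorded in the same way whether that relative is a parent or an aunt. Modified Braun needs both distinctions, and the ASAS arthritis item needs the first.

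Section 2.3 includes a comparison of four existing strategies and the BACKPACS model, in order to choose the most clinically effective one. Modified Braun is one of the four and refers at four of ten items, so an item scored wrongly can move a participant across the cut. This is not a detail that the statistical analysis plan can settle later, because it concerns data collection. Separately, the joint list and the stated maximum counts in the same table do not agree.

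**Working it through.** **1. Arthritis: what is needed against what is listed**

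| Use | What it needs | What Table 6 lists |
|---|---|---|
| Modified Braun (Table 3) | current or past arthritis | examination of joints at the visit |
| ASAS classification (Appendix 1) | past or present synovitis, physician-diagnosed | examination of joints at the visit |
| ASAS referral strategy (Table 3) | arthritis, with no statement on timing | examination of joints at the visit |

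The personal-history list has seven items and arthritis is not one of them. The dactylitis row of Table 6 does ask about past disease, so the form collects history for neighbouring features. The patient questionnaire (Section 4.1.3) names only psoriasis and NSAID response as clinical features, so it does not fill the gap. The participants exposed are those with past arthritis and nothing to find on the day.

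**2. Family history**

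Modified Braun needs an affected first-degree relative. Table 6 gives a yes/no for both degrees together and a count of relatives. The count does not identify degree: a count of 1 fits a sibling or a grandparent equally. A participant who answers no is scored correctly; the ambiguity is confined to those who answer yes. The Appendix 1 item accepts both degrees, so the ASAS family-history item is unaffected.

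**3. Direction of the possible errors in modified Braun (cut at 4 of 10)**

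- Missed past arthritis lowers the score by 1. It changes the result only when the recorded score is 3 and the true score is 4.
- A second-degree relative counted as first-degree raises the score by 1. It changes the result only when the recorded score is 4 and the true score is 3.

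The two errors run in opposite directions. The protocol gives neither the share of participants at these scores nor the frequency of either feature, so the net effect cannot be computed. The planning figures give only a scale: 14% of 720 is 0.14 × 720 = 100.8, about 101 cases, so each case classified wrongly moves sensitivity by 1/101, about 1 percentage point. Each of the other 720 − 101 = 619 participants moves specificity by 1/619, about 0.16 percentage points.

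**4. Joint count**

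The stated maxima are 66 swollen and 68 tender. The listed ranges are:

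- "Joints assessed include temporomandibular joint, (0-2) Sternoclavicular joint (0-2), Acromioclavicular joints (0-2), Glenohumeral(s) (0-2), Elbow(s) (0-2), Wrist(s) (0-2": 6 × 2 = 12
- "Metacarpal phalangeal joints (0-10), Finger Proximal interphalangeal joint (0-10": 10 + 10 = 20
- "hip(s) (tender score only 0-2), knee(s) (0-2), ankle(s) (0-2), metatarsal phalangeal joints (0-10), toe PIP(s) (0-10": 2 + 2 + 2 + 10 + 10 = 26 tender; without the hips, 24 swollen

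Tender: 12 + 20 + 26 = 58, which is 68 − 58 = 10 short. Swollen: 12 + 20 + 24 = 56, which is 66 − 56 = 10 short. Counting the hips in both gives 58 and 58. Neither reading reproduces 66 and 68.

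**The case against.** The strongest reply is that Table 6 summarises the form and is not the form itself. The assessment is described as semi-structured, the eCRF is not shown, Appendix 1 already defines arthritis as past or present, and the footnote already separates the two degrees of relative. The fields may therefore exist. That is why the conclusion is that items could be mis-scored. A reader might infer that they are mis-scored, or that past arthritis is missed in everyone who has had it, and the protocol does not show either. What stands is that Section 4.1.4 presents Table 6 as the proforma, and nothing elsewhere in the protocol names the missing fields.

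Other stronger readings also fail:

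- **That sites cannot produce a 66/68 count.** The row names the instrument, and its list is introduced in a way that need not be exhaustive, so staff in specialist rheumatology clinics may well perform the full count. Nor does any rule turn the joint total into the yes/no arthritis item. The short list would matter to that item only for arthritis confined to unlisted joints.
- **That the ASAS referral strategy is equally exposed.** Table 3 does not ask for past arthritis there, and the rule is met by any one of eight features. With the specificity of 0.16 in Table 1, most people without the disease are already positive.
- **That a percentage of participants misclassified can be given.** Any such figure would need the share of participants near the cut and the rate of mis-recording. The protocol has neither.
- **That the main results are at risk.** Baraliakos uses NSAID response, CRP, morning stiffness and HLA-B27. The primary reference standard is the rheumatologist's diagnosis and is not scored from these fields. The protocol expects either Baraliakos or BACKPACS to go forward.

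The exclusion of people with an existing inflammatory arthritis diagnosis (Section 3.4.2) also reduces the group with relevant past arthritis. It does not clearly remove someone with a resolved episode and no standing diagnosis.

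**Conclusion.** The point holds as a gap in data capture. As listed in Table 6, two of the ten modified Braun items (arthritis and first-degree family history) and the past part of the ASAS arthritis item cannot be derived as Table 3 and Appendix 1 define them. Modified Braun could be mis-scored in the secondary comparison of strategies, and past arthritis could be missed in the secondary reference standard. The number affected cannot be derived from the documents and is narrowed by the arthritis exclusion. The first co-primary objective, validation of Baraliakos, does not use these items. The conclusion assumes that the form follows Table 6 as the protocol says; if the eCRF already holds both fields, only the table needs correcting. The ten-joint shortfall in each count is certain as arithmetic but minor in consequence.

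**What to change.** 1. Add to the personal-history list in Table 6 an item for arthritis diagnosed by a physician, current or past.
2. Record family history separately for first-degree and second-degree relatives. Score modified Braun on first-degree relatives only, and the Appendix 1 item on both.
3. Reconcile the joint list with the named SJC66/TJC68 instrument, so that the listed joints add up to 68 tender and 66 swollen, or restate the instrument and its ranges.

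The cost is a short edit to the proforma and eCRF. Participants already assessed would need a query for the two history items. If any were examined on the shorter joint list, their counts cannot be completed afterwards and should be identified as such. The earlier the change is made, the fewer queries are needed.

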3.1.2 Reference standard

Page 16 of 53

IDEAL BACKPACS Protocol Final Version 1.1 date 09-Oct-I2024

The primary reference standard will be clinical diagnosis by a rheumatologist reviewing all clinical and diagnostic parameters. Diagnostic confidence will be reported on an 8 point Likert scale as described in Table 2, with scores of 7 or 8 considered as diagnosed with axSpA. Reviewing rheumatologists will not be provided with any results from existing screening tools to inform the presence or absence of axSpA.

The reference standard for the primary analysis will be comprised of a confirmed diagnosis (a score of 7 or 8) versus normal or equivocal (a score from 1 to 6).

Table 2: Pre-defined reference standard for a diagnosis of axSpA

Diagnostic category	Score	Definition
Normal	1	axSpA definitely not present
Normal	2	axSpA not present
Equivocal	3	axSpA probably not present
Equivocal	4	axSpA possibly not present
Equivocal	5	axSpA possibly present
Equivocal	6	axSpA probably present
Diagnosed	7	axSpA present
Diagnosed	8	axSpA definitely present

The ASAS axSpA classification will be a secondary reference standard (Figure 2).

[figure not shown]

Figure 2: ASAS classification criteria for axial spondyloarthritis (axSpA)

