4.1.6 PI assessment and reporting

The laboratory results, clinical assessment, x-rays and MRI reports will be sent to the local PI. The local PI (or delegate) will then review all clinical and diagnostic parameters. Diagnostic confidence will be reported on an 8 point Likert scale as described in Table 2 (Section 3.2), with scores of 7 or 8 considered as diagnosed with axSpA. Reviewing rheumatologists will not be provided with any results from existing screening tools to inform the presence or absence of axSpA. The ASAS axSpA classification [1] (see 3.1.2 Reference standard) will be a secondary reference standard.

The participant will be informed by the local PI (or delegate) whether or not they are likely to have axSpA or whether their back pain is likely to be due to non-inflammatory causes. A summary of the laboratory, x-ray and MRI reports will be forwarded to the participant's GP. The participant will also receive publicly available advice leaflets/website links, related to their diagnosis from the research site team.

If axSpA diagnosis is unclear, then it will be flagged to the GP in this letter. For patients with an equivocal likelihood of axSpA, further clinical investigation might be required in the future time in either primary or secondary care (at the discretion of the patient's primary care team).

All reports will be entered to the study database by site clinicians, or their delegates. This will include any diagnostics of serious conditions.

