4.2.2 Imaging

Radiographs

For participants aged 18 and over, conventional SIJ plain x-rays will be taken.

Page 32 of 53

IDEAL BACKPACS Protocol Final Version 1.1 date 09-Oct-2024

MRI

MRI scans will be acquired according to a dedicated imaging protocol. Participants will have an MRI scan of their SIJ and whole spine (30 min scan) arranged within 4 weeks (where possible) of clinical assessment. For some secondary care sites, the MRI scan may be on the same day as the clinical assessment, if there is capacity. MRI scans will be acquired according to a dedicated imaging protocol which will be provided separately.

Briefly, SIJ MRI acquisitions will be performed in modified coronal plane (aligned with the long axis of the SIJ), using small field-of-view imaging and consistent resolution (matrix size) between the acquisitions.

We will acquire:

- T2-weighted STIR or turbo STIR imaging
- T1-weighted turbo spin echo imaging a
- T2-weighted Dixon turbo spin echo imaging (repeated with two effective echo times).

For the spine imaging, we will cover the whole spine in the sagittal plane, using either two or three blocks, using (i) T2-weighted STIR or 'turbo' STIR imaging and (ii) T1-weighted turbo spin echo imaging.

Data upload

Image data will be acquired in DICOM format and pseudo-anonymised by individual sites, before being uploaded to the XNAT platform for image storage and curation. Each site will have their own folder on the XNAT platform to minimise the risk of data leaks between sites.

Scan interpretation

All scans will be read by two consultant radiologists on the XNAT platform. If discrepancies exist regarding the overall impression of whether axSpA is present (i.e. whether the patient is 'imaging positive') across the MRI and x-ray, a third consultant radiologist will perform an additional read and make a final decision on the appropriate category.

The following will be included in the x-ray report:

Modified New York criteria grade 0-4 for each SIJ.

The following will be included in the MRI report:

- Description of oedema and structural features (fat metaplasia, erosions, ankylosis) in SIJs – yes/no for each.
- Interpretation according to ASAS specifications (bone marrow oedema in typical location 'highly suggestive' of axSpA) - yes/no for MRI positivity
- Are there unequivocal features of spinal inflammation? yes/no

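### An unclear NSAID response, an item in three of the index tests, is settled by telephone at 1 week with nothing keeping blood and imaging results from the caller

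*Protocol*

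**What the plan says.** The stated protections are on the reference side. Section 3.1.2 says "Reviewing rheumatologists will not be provided with any results from existing screening tools to inform the presence or absence of axSpA", and section 4.1.6 repeats this. Section 4.1.5 blinds the central X-ray and MRI readers to clinical and laboratory data. The synopsis row for randomisation and blinding reads n/a.

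NSAID response is part of several index tests. Section 3.1.3 (Table 3) says of Baraliakos: "Assesses 3 clinical variables. If 2 or 3 of these variables are present", or if HLA-B27 is positive, referral is suggested. One of the three is "improvement in pain with NSAIDs after 48 hours". Response to NSAIDs is also an item in modified Braun and ASAS, and section 2.2 makes the Baraliakos predictors candidates for BACKPACS.

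Table 6 in section 4.1.4 records the item as the participant's own yes/no report. A further step applies "Only if NSAID response is not completely clear": a course of at least seven days, "with telephone evaluation of NSAID response from research team at 1 week".

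On timing, bloods and X-ray are taken at the clinic visit (section 4.1.4). Section 4.2.2 adds: "For some secondary care sites, the MRI scan may be on the same day as the clinical assessment, if there is capacity". Any spinal or sacroiliac MRI from the last 12 months is asked about in clinic. Section 4.2.3 sends a local MRI report to the site PI, and section 4.1.6 says: "The laboratory results, clinical assessment, x-rays and MRI reports will be sent to the local PI".

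**The concern.** In a diagnostic accuracy study, review bias can run both ways. The protocol deals with one direction, where the index test influences the diagnosis. It does not deal with the other, where results that feed the diagnosis influence how an index item is recorded.

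Most clinical items are protected by sequence, because they are collected at or before the visit at which blood and X-ray are taken. The 1-week NSAID answer is the self-reported item that the protocol allows to be completed afterwards. It is reserved for unclear answers, which are the ones most open to how a question is put. The caller belongs to the site research team, which may by then hold the blood and X-ray results and, less often, an MRI report.

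The accuracy of Baraliakos (first co-primary objective), the selection of variables for BACKPACS (second) and the comparison of strategies all use this item. A larger sample would not remove such a bias, and an analysis plan agreed before database lock could not restore blinding that was never in place.

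**Working it through.** 1. **The plan's own figures.** Section 5.2 assumes 14% prevalence, sensitivity 90% against a bound of 79%, and specificity 65% against 58%, with over 90% power. No alpha is stated; two-sided 5% is assumed here. Allowing for 20% without full data, 720 × 0.8 = 576, which is 81 cases and 495 non-cases. With power = Φ(|p1 − p0|√n / √(p1(1 − p1)) − 1.96):
   - sensitivity: 0.11 × √81 / √(0.90 × 0.10) = 3.30, giving 91.0%;
   - specificity: 0.07 × √495 / √(0.65 × 0.35) = 3.27, giving 90.4%.

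   The stated power reproduces with this approximation. Stricter formulas give less for sensitivity, but power is not the issue here. The figures only set the scale.

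2. **What the caller can know on day 7.** Take the clinic visit as day 0 and assume that the course starts then.
   - Bloods and X-ray: done on day 0, so results may be back. Participants under 18 have no X-ray.
   - Research MRI on the clinic day: a local report is possible, in the usual NHS time frame. No number of days is given, and the central research read might come some weeks later (section 4.2.3).
   - Research MRI on another day: participants are asked to stop NSAIDs for one week beforehand (section 4.1.5), so the earliest date is day 7 + 7 = 14, after the call.
   - MRI from the previous 12 months: may be known from day 0.

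   Blood and X-ray are therefore the main route, and MRI the less frequent one.

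3. **When the item decides the Baraliakos result.** Only if HLA-B27 is negative and exactly one of morning stiffness and raised CRP is present. An HLA-B27-positive participant is already Baraliakos-positive whatever the NSAID answer.

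4. **Direction.**
   - Non-cases in the decisive group have a negative HLA-B27 and usually unremarkable imaging. Knowing this would push an unclear answer to no, the test to negative and specificity up.
   - Cases in the decisive group also have a negative HLA-B27. Knowing that could push to no and lower sensitivity, while positive imaging could push to yes and raise it. The net effect is uncertain.

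5. **Size, with assumed inputs.** The protocol gives none of these.
   - Non-cases: stiffness 0.50, raised CRP 0.10, HLA-B27 0.08. Decisive share = (0.50 × 0.90 + 0.50 × 0.10) × 0.92 = 0.46.
   - Cases: stiffness 0.65, raised CRP 0.35, HLA-B27 0.70. Decisive share = (0.65 × 0.65 + 0.35 × 0.35) × 0.30 = 0.16.
   - Unclear response 20–40%; net share of those answers moved by knowledge of results 10–20%.
   - Shift = unclear share × share moved × decisive share.
   - Specificity: 0.20 × 0.10 × 0.46 = 0.009 up to 0.40 × 0.20 × 0.46 = 0.037.
   - Sensitivity, only if every net shift were favourable: 0.20 × 0.10 × 0.16 = 0.003 up to 0.40 × 0.20 × 0.16 = 0.013.

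   The formula has no factor for the chance that the caller has actually seen the results, so it takes that chance as 1. The shift falls in proportion as the chance falls, to nil if no caller has seen them.

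6. **Effect on the likelihood ratio.** At planning values LR+ = 0.90 / 0.35 = 2.57. With sensitivity held and specificity raised by the ceiling range, LR+ = 0.90 / (0.35 − 0.009) = 2.64 to 0.90 / (0.35 − 0.037) = 2.88.

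7. **Dependence on assumptions.** A looser set (unclear 10–50%, decisive 10–40%, moved 10–30%) gives 0.1 × 0.1 × 0.1 = 0.1 points up to 0.5 × 0.4 × 0.3 = 6.0 points. The assumptions, not the protocol, set the figure.

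**The case against.** Much of the case on the other side stands.

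- **The item is self-reported.** A reader might infer that the site team grades NSAID response. Table 6 does not support that: staff elicit and record the participant's yes or no, and only when the response is unclear. What remains is that a person resolving an unclear answer by telephone can still steer it.
- **There is an earlier record free of results.** The participant questionnaire, sent for completion before the clinic visit, also asks about NSAID response (section 4.1.3). That would settle the matter if the protocol named it as the record that scores the index tests. The protocol does not say which record does.
- **MRI will seldom be known at the call.** The one-week NSAID stop and the reporting times see to that, except with a clinic-day or earlier MRI.
- **Blood results belong to the strategy.** CRP and HLA-B27 are Baraliakos components, and Table 3 says the strategy needs follow-up after the first appointment. A GP might therefore also know them when asking about NSAIDs. The information that would be foreign to intended use is the X-ray and MRI.
- **Late editing is not documented.** A reader might infer that proforma items are open to change once results arrive. No text says so. Section 8.3.1 provides a full audit trail and leaves data handling to a Data Management Plan that is not shown. What can be said is that the protocol states no lock.
- **The n/a entry** is in a combined synopsis row, and the body does describe blinding. The entry is incomplete rather than evidence that blinding was ignored.

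The gap itself is not answered by any of this: no sentence keeps results from the person who makes the 1-week call, and who knows what during data collection is a matter for the protocol.

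**Conclusion.** The point holds as a limited gap in study conduct. The reference side is blinded; the collection of the 1-week NSAID answer is not. Inflated specificity is the most plausible consequence.

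A reader might infer that sensitivity and specificity are both inflated. The documents do not support that: HLA-B27-positive participants are already Baraliakos-positive, and a known negative HLA-B27 could lower sensitivity.

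The size cannot be derived from the protocol and is probably small. The range of 0.9 to 3.7 points for specificity is a ceiling for its inputs. It rests on assumed item frequencies, an assumed unclear share, net shifts that are all favourable, and results that are always seen. Its upper end is about half of the 7-point gap between 65% and 58%, but that gap is a margin for power, not a tolerance for bias. At planning values, LR+ exceeds the threshold of 2 cited in section 1.2 with or without the shift. The case for change is that the fix costs very little and cannot be applied after the data are collected.

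**What to change.** In section 4.1.4 and Table 6:

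- State that the 1-week NSAID answer is collected through the existing REDCap participant link, or by a team member who has not viewed that participant's blood or imaging results, and that it is locked and time-stamped on entry.
- Name which NSAID record (questionnaire, clinic or 1-week) scores each index test.
- Require the clinic proforma to be locked before results are opened.

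In the synopsis, replace n/a under blinding with a statement of who is blind to what.

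Do not exclude answers because of their time-stamp. The primary analysis uses complete data only (sections 4.2.4, 5.3 and 5.4), so that rule could selectively remove the unclear responders. Flag answers recorded after results were seen, and examine them in a sensitivity analysis.

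The cost is one survey link, a form lock and minor site administration, with no extra visit. Separately, Table 3, Table 6 and Appendix 1 differ on the time at which NSAID response is judged (48 hours, 24 to 48 hours, one week) and must be reconciled.
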